For the comparison of effectiveness between different doses of vitamin E (primary aim 1), the primary biochemical end point will be used. We assume a response rate of 45% with the 800 IU/d dose (similar to that seen at the PIVENS trial), a 10% response rate to the 200 mg/d dose and a 20% response to the 400 mg/d dose. Under these assumptions, a sample size of 25 patients per group will give a power of 80% to detect a linear trend with statistical significance of 5% (Cochran-Armitage test). To account for possible drop-out and loss to follow-up, we are aiming to recruit 30 patients per group or an overall of 90 patients in the study.

As the sample size calculation is limited by the absence of published data, we will re-assess our calculations after 10 patients have been enrolled in each arm, and again after 20 have been enrolled

Human subject protections

Rationale for subject selection

The study is designed to enroll patients with NAFLD that can be potentially benefit from treatment. Currently, there are no reliable non-invasive markers that accurately distinguish NASH from steatosis only, although the latter seems to carry a more favorable prognosis. For patients with steatosis only, it is unclear whether treatment can improve their disease and prevent progression to NASH. In most clinical trials with histological end points, patients with steatosis only were excluded as they cannot show significant histological

improvement. In this study, with a primarily scientific outcome, we are interested in studying the effect of vitamin E on these patients as well and we consider the intervention to be low-risk enough to allow us to recruit all patients with NAFLD.

The exclusion criteria for the study are mainly geared towards limiting enrollment to patients for whom treatment is considered safe and that have no confounders that would limit the analysis of the results. There are no limitations based on race or ethnicity. However, we anticipate that very few patients of African ancestry will be enrolled, because of the scarcity of NAFLD in these patients and their apparent "protection" from liver fat accumulation.

We intend to enroll women as well as men and do not foresee a marked difference by gender. We exclude pregnant women and require stable contraception from participants, because of the interventions, blood draws and imaging using radiation. Furthermore, pregnancy has an effect on metabolic parameters and fat handling and will not allow analysis of the data. Similarly, we choose not to enroll breast-feeding women as the dietary recommendations for them are different from those given to the general population and will limit the ability to analyze the data.

Enrollment in this study is limited to adult patients as the pediatric form of NAFLD has unique clinical and histological features and the choice of therapies may be different.

Recruitment strategy

Patients with NAFLD who have been followed at the LDB clinic will be offered participation based on eligibility. New patients are continuously evaluated at the clinic and will be enrolled as well. We will inform local primary care providers, gastroenterologists, hepatologists and free clinics of the availability of the protocol and eligibility criteria. Patients seen by the Liver Service as consult cases will be offered participation in the protocol if deemed eligible and only with the agreement of the referring physician and the principal investigator for the referring protocol. We aim to recruit 90 patients for the study within 3 years.

Informed consent process

The initial screening visit to assess eligibility for the protocol will be done under protocol 91-DK-0214, "Evaluation of Patients with Liver Disease"; only eligible patients will then be consented into this protocol. Written informed consent will be obtained from the participant prior to any study procedures or treatments. The Principal Investigator or other designated qualified protocol investigators will explain the study in language understandable to the subject. Sufficient time and opportunity will be given for discussion of the research as well as to answer any questions they may have, taking care to minimize or eliminate the perception of coercion or undue influence. The participant and the investigator will sign the current IRB-approved informed consent documentA copy of the consent will be given to the subject for future reference. The signed documents will be sent to the Medical Records Department for placement in the subject's permanent CC medical record. The consent process will additionally be documented in the electronic medical record (CRIS).

We anticipate the enrollment of Spanish speaking subjects into this study for which English consents have been fully translated.

Evaluation of benefits and risks

Benefits

Most patients with NAFLD are overweight and have some degree of insulin resistance. For these patients lifestyle modification with dietary consultation aiming at weight loss and a moderate exercise regimen is of proven benefit, is considered standard medical care³² and conforms to the recommendations for the population as a whole^{33, 34}. The target level of exercise, 150 minutes of moderate intensity per week, is the minimum recommended for all adults.

Currently, there are no reliable non-invasive markers that accurately distinguish NASH from steatosis only, which carries a much more favorable prognosis. Even the presence of elevated liver enzymes in patients with liver fat predicts the presence of NASH in only 55%³⁵ to 62% (NASH-CRN data, unpublished) of cases. Thus, a liver biopsy is essential for proper staging, as well as to provide tissue for the scientific studies.

Patients with NAFLD who did not previously have a liver biopsy can benefit from one; however, a liver biopsy is not considered essential in routine management of NAFLD. Repeat liver biopsies are not routinely performed on patients with fatty liver disease outside of the research context but in this study are crucial to define the histology and to allow evaluation of response mechanism.

Vitamin E therapy for NASH has been shown to improve fat deposition in the liver, decrease liver enzymes and reduce histological evidence of cellular injury, without affecting insulin sensitivity³. Thus, although it is not yet approved as standard medical treatment for NASH, there is clearly a potential benefit to the patients.

Risks and Discomforts

Physical exercise. Adults who exercise are inherently at a higher risk for exercise-induced musculoskeletal injury, but lower risk for non-leisure time injuries; however, the risk of injury with a supervised program and moderate intensity is not much different for that of sedentary adults³⁶. The risk of a major cardiac event during exercise is small with moderate-intensity activity and there is no clear evidence to suggest a need for screening of asymptomatic individuals. In this study, we adopt the screening recommendations of the American Heart Association for diabetic patients who start an exercise program³⁷ and apply them to the whole study population.

Exercise induced hypoglycemia can occur in diabetic patients treated by insulin or insulin secretagogues, especially those maintaining tight glycemic control. An endocrine consult will be requested on these patients to assess the need for dose modification and the patients will be encouraged to monitor their blood sugar levels routinely.

Diet. The dietary intervention in this study is aimed at achieving a balanced diet with mild caloric deficit and gradual weight reduction, and conforms with the general

recommendations for obese or diabetic patients. No significant complications or risks are anticipated from this diet.

Liver biopsy. Patients will undergo 3 liver biopsies in this protocol; one after the lifestyle modification phase, a second after 4 weeks of vitamin E therapy, and an exit biopsy at the end of the study. The liver biopsy will be performed when the patients are admitted as inpatients to the Clinical Center for the extensive evaluation detailed above.

The major side effects of liver biopsy are pain, bacteremia, puncture of another organ and bleeding³⁸. Local pain and discomfort at the liver biopsy site occur in about 20% of persons undergoing percutaneous liver biopsies. This is transient (lasting one to twelve hours) and usually mild, rarely requiring analgesics. Bacteremia occurs in 1-2% of persons undergoing liver biopsy. In the absence of bile duct obstruction, this is almost always self-limited and is rarely symptomatic. Inadvertent puncture of another organ such as lung, colon, gall bladder, kidney and adrenal gland can occur during liver biopsy. All biopsies will be performed after a bedside ultrasound examination by the performing physician to identify internal organs and select and optimal site and direction for the biopsy. Significant bleeding after liver biopsy is the most serious side effect of this procedure. In the absence of blood coagulation defect or hepatic malignancy, significant bleeding is rare, occurring in less than one in a thousand cases of liver biopsy. Death due to bleeding after liver biopsy has been reported to occur in less than 1/10,000 cases. At the NIH Clinical Center, the Liver Diseases Branch has performed approximately 150 liver biopsies each year for the past 25 years. During this time, two patients have died as a result of liver biopsy. One patient had cirrhosis and advanced hepatocellular carcinoma. The second patient had Gaucher's disease with hepatic involvement and severe coagulopathy. Both patients died after surgical attempts to stop the bleeding were unsuccessful.

Adipose Tissue Biopsy. The major risks/discomforts are represented by pain, bruising, hematoma, infection, scarring, and localized lipodystrophy. The procedure will be performed under sterile technique to minimize the chances of infection. Ice will be applied to the site immediately after the procedure to limit bruising, swelling and tenderness. After subcutaneous tissue biopsy, patients will be monitored by nurses. Post-biopsy, the needle site will be cleaned and covered with gauze and translucent dressing tape. Study participants will be instructed to report to the clinical staff any changes at the biopsy site including bleeding, secretion, erythema, pain, and signs and symptoms of infection. Study participants will be instructed to self-monitor the puncture site after discharge from the Clinical Center.

Frequent phlebotomy. To document the baseline and to monitor the effects and toxicities of treatment, frequent blood sampling will be required. Patients will have 15-20 venipunctures during the period of evaluation and the first 6 months of therapy and 4 venipunctures per year in the extended treatment phase. Each venipuncture will be for 32 to 150 ml of blood. However, no more than 550 ml or 10.5 ml per kg (the lower of the two) will be drawn from any one person during any eight-week period.

Imaging studies.

1) **DEXA scan**. Patients will undergo 2 DEXA scans in the first year of treatment and another test at the end of the extended treatment phase, to assess whole body composition. The effective dose of radiation that patients will receive

- from a single study is 0.5 mrem; thus the total effective dose from DEXA for the duration of the study is 1.5 mrem.
- 2) *MRI scans*. Patients will undergo 5 MRI scans in the first year of treatment and another test at the end of the extended treatment phase, to determine the amount of liver fat, liver volume and subcutaneous and visceral fat. While serial MRI scanning is thought to be safe, the procedure may cause anxiety in some patients since current equipment used at the Clinical Center uses a closed tube. Patients will be offered sedatives such as Valium if they express worry about being in a closed space.

All female patients with childbearing potential will have a pregnancy test prior to any imaging test involving ionizing radiation.

IVGTT. Patients will undergo 3 IVGTT tests in the first year of the study and another one at the end of the extended treatment phase. Patients will have two intravenous catheters placed for the procedure, one for the infusion of glucose and insulin and the other for blood drawing. Patients may experience pain from intravenous catheter insertion or may feel a burning sensation during the rapid injection of glucose. There is a small risk of hypoglycemia from the short period of insulin infusion, although it is extremely rare and blood glucose will be monitored frequently during the test. With mildly low blood sugars (<50 mg/dl), subjects may get hungry, may become drowsy or sweaty. With blood sugars below 30 mg/dl, subjects may be difficult to arouse or have seizures. We do not anticipate significant hypoglycemia as most or all of the patients are predicted to have some degree of insulin resistance. Nevertheless, a physician or nurse will be present during this test for the first hour of the test (including the first thirty minutes following insulin administration) to monitor for signs of significant hypoglycemia. If significant hypoglycemia occurs it will be treated with intravenous dextrose or glucagon according to clinical evaluation. The total amount of blood that will be drawn during this test will be 120 to 150 ml.

Vitamin E treatment. The dose of vitamin E used in this study is lower than the recommended upper limit of supplement intake (1500 IU/d)⁹. Some studies of vitamin E supplementation for primary or secondary prevention of disease suggested increased mortality or risk of hemorrhagic stroke¹². Two meta-analyses^{39, 40} suggested slight increased mortality in patients treated with high-dose vitamin E. However, these works were criticized for several reasons and the studies selected for the meta-analyses included mostly patients with chronic diseases. A recent meta-analysis using all trials found no excess mortality risk⁴¹. Furthermore, these studies focused on the use of vitamin E for disease prevention (a scenario where little or no risk would be tolerable), whereas our trial uses vitamin E as a proven treatment for an existing disease. In the PIVENS trial³, no excess adverse events were noted in the vitamin E in comparison to the placebo arm.

As some studies suggest an effect of vitamin E on platelet aggregation⁴², and given the possible association with hemorrhagic stroke, we exclude patients with high bleeding risk, such as those with coagulopathies, use of anticoagulants, thrombocytopenia or known platelet dysfunction. Furthermore, due to the possibility of increased risk of gastrointestinal bleeding, patients with a pre-existing history of iron deficiency anemia secondary to gastrointestinal sources are excluded. On the other hand, vitamin E supplementation is not associated with changes in standard parameters of bleeding tendency, including PT, PTT,

platelet count and bleeding time^{43, 44}, rendering these useless as a tool for safety monitoring during vitamin E treatment. However, if during the study the platelet count or PT/PTT cross the thresholds for study inclusion (i.e. platelets <70,000, PT/PTT prolonged by >=3 seconds), treatment will be stopped and patients withdrawn from the study.

Recently, data from extended follow-up of the SELECT trial⁴⁵ suggested increased risk for the diagnosis of prostate cancer in patients treated with vitamin E. This is in contrast to the findings of two other similar studies^{46, 47} which did not show such an effect. Our patients are anticipated to be significantly younger than the study population in SELECT (median age 62); furthermore, risk for prostate cancer appeared to increase numerically only after more than 3 years of treatment. We will monitor PSA levels every 12 months on male patients in our study. Screening for prostate cancer may lead to further evaluation of abnormal results, including referrals, blood tests and possible invasive procedures. There is also a risk of detecting prostate cancers that are not destined to become clinically significant. The risks and benefits of screening with annual PSA testing will be discussed with all male participants prior to enrollment and patients will have the option to elect not to be screened.

Adverse event reporting and data monitoring

Reportable events will be tracked and submitted to the IRB as outlined in Policy 801.

The PI will immediately report SAEs to the Sponsor according to the requirements of 21 CFR 312.64(b) and as agreed upon with the sponsor. The PI will record nonserious AEs and report them to the Sponsor according to the timetable for reporting specified in the protocol (21 CFR 312.64(b).

All serious, unexpected, suspected adverse reactions (SUSAR) will be reported to the sponsor within 15 calendar days. All unexpected suspected adverse reactions resulting in death or life-threatening events will be reported to the sponsor within 7 calendar days. The investigator may also be responsible for completing an FDA MedWatch 3500 form and additional information for a follow-up SAE report as information becomes available.

Summary of adverse events and efficacy data will be provided in annual reports to the FDA.

Monitoring

Safety monitoring will be maintained by weekly meetings of the investigators to review clinical data on patients seen in the outpatient clinic and maintenance of individual flow sheets on each patient. Laboratory and imaging test results will be reviewed routinely by the treating physician, the principal investigator and the study nurse.

As required by FDA 21 CFR 312.50, this study will be monitored to ensure compliance with the protocol and applicable regulatory requirements. Monitoring results will be reported to the Principal Investigator/Sponsor for further reporting to the FDA consistent with applicable regulations. The specific monitoring plan will be developed with the Principal Investigator and frequency of monitoring visits will be determined by such factors as study enrollment, data collection status and regulatory obligations. Study

documents and pertinent hospital or clinical records will be reviewed to verify that the conduct of the study is consistent with the protocol plan.

Collection and storage of human specimens or data

Patients will have serum stored from selected time points during this study. These specimens will be used for repeat testing (in case of missing samples) or for special tests as needed (such as for serum cytokines or adipokines). Serum samples will be stored at the NIDDK clinical core laboratory inside locked freezers in locked rooms and will be labeled by coded unique identifiers without personally identifiable information. The code to these samples will be maintained by the clinical core personnel.

Liver and adipose tissue biopsy samples may be stored if residual tissue is available after routine samples are taken for routine histological staining and evaluation. PBMCs will be stored until they are used for NK/NKT cell and gene expression analysis. RNA or protein that is extracted from these samples will be stored as well. The samples will be stored in a locked freezer in a locked room at the LDB laboratory and will be labeled by a coded unique identifier without personally identifiable information. The code to these samples and their location will be maintained by the primary investigator and the laboratory manager.

Access to stored samples and the identifiers will only be provided to the principal or associate investigators, and only with the written approval of the principal investigator and the branch chief. If samples are to be evaluated by outside collaborators in the future, they will be coded and all identifying data removed from the samples. The code to identify samples and associate them with patient identity will be maintained by the principal investigator and not shared with outside collaborators.

Research records and data as well as liver biopsy slides, biopsy reports, liver tissue and sera will be stored indefinitely in our locked offices and freezers, the medical record department and the pathology department. These materials will be protected and tracked by standard operating procedures in the medical record and pathology departments as well as a compulsive filing system in our locked offices and freezers. There will be redundant storage of clinical information in the medical record department and our offices. Likewise, there will be redundant storage of biopsy information and materials in the pathology department and our offices. This should minimize the risk of loss or destruction of information and specimens. If that were to occur we would report it to the IRB. We do not plan to destroy this personal medical information or the liver biopsy specimens or research subject sera after completion of the study because it may be critically important for physicians (here or elsewhere) to have access to this information when caring for these patients in the future.

Remuneration/compensation

Compensation will be provided to subjects for participation in some of the research procedures and tests in the study, according to the following schedule:

For the baseline (week 0 of run-in phase) MRI\$ 60.00 For the 1st inpatient hospital admission including: DEXA scan.....\$ 10.00 MRI.....\$ 60.00 FSIVGTT \$ 70.00 Adipose tissue biopsy.....\$ 50.00 Resting Energy Expenditure......\$ 25.00 Total compensation for the admission...... \$ 335.00 For the 2nd (week 4) inpatient hospital admission including: MRI.....\$ 60.00 FSIVGTT..... \$ 70.00 Liver Biopsy.....\$ 280.00 Adipose tissue biopsy.....\$ 50.00 Resting Energy Expenditure......\$ 25.00 Time\$ 80.00 (2 nights/\$ 40.00 per night) For the 3rd (week 24) inpatient hospital admission including: DEXA scan.....\$ 10.00 MRI.....\$ 60.00 FSIVGTT \$ 70.00 Resting Energy Expenditure......\$ 25.00 For the final (Week 144) inpatient hospital admission including: DEXA scan\$ 10.00 MRI \$ 60.00 FSIVGTT \$ 70.00

Vitamin E for Non-Alcoholic Fatty Liver

Adipose Tissue biopsy	\$ 50.00
Resting Energy Expenditure	\$ 25.00
Time	\$ 120.00 (3 nights/\$ 40.00 per night)
Total compensation for the admission	\$ 615.00
Total overall (maximal) study compensation	\$ 1,780.00

No remuneration is offered for taking vitamin E, outpatient visits, blood tests, nutritional consults and study questionnaires.

Patients may also be eligible for reimbursement of travel expenses based on standard Clinical Center and LDB criteria.

References

- 2. Cusi K. Role of insulin resistance and lipotoxicity in non-alcoholic steatohepatitis. Clin Liver Dis 2009;13:545-63.

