During the randomized vitamin E treatment phase, patients will be continue to be seen by the nutritionist every 8 weeks for individual follow-up visits and to reinforce components covered during the initial 12 week lifestyle intervention. During the extended treatment phase, the patients will be seen by the nutritionist every 12 weeks. Patients will complete the 3-day food intake diary and IPAQ every 24 weeks during the randomized treatment and extended treatment phases. The data obtained from these diaries and questionnaires will be used to ensure that differences in outcomes observed between the different vitamin E groups are not due to differences in adherence to lifestyle changes. Although part of the effect of treatment may be due to lifestyle intervention, it should affect all treatment groups in a similar manner and the effect of vitamin E will be deduced from the dose response.

Detailed in-patient assessment

At the beginning of the randomized-dose treatment phase, patients will be admitted to the Clinical center for a detailed histological, physiological and biochemical analysis, including:

- 1. History and physical examination: including vital signs, weight and anthropomorphic measurements.
- 2. Fasting blood tests: chem-20, GGT, CBC, PT, PTT, serum insulin, c-peptide, lipid panel, apolipoproteins, total free fatty acids, hemoglobin A1c, alpha-fetoprotein, ferritin, iron, transferrin saturation, immunoglobulins, TSH, C-reactive protein, PSA and vitamin E levels
- 3. Research blood: 10 ml of serum will be separated from collected blood and stored in 2 separate aliquots in -80°C for determining serum levels of hormones, cytokines and adipokines, injury markers (such as CK-18 fragments), and for archival storage. 10 ml of plasma will be separated from collected blood and stored at -80°C for analysis of oxidative stress measures.
- 4. NKT and NK cell analysis: 40 ml of blood will be drawn for analysis of NKT and NK cell phenotype and effector function. Additional 8 ml of serum tube (8 ml) will be used to provide autologous serum for in vitro functional assays. The frequency of performing these assays is detailed in table 1.
- 5. Urine tests: urinalysis, pregnancy test (for women of child-bearing potential) and 24-hour urine collection for creatinine clearance and protein and uric acid

excretion. A 5 ml urine sample will be stored at -80°C for oxidative stress measurements.

6. Imaging:

- a. Magnetic resonance imaging (MRI):

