- 3. Presence of definite or probable drug-induced liver injury. In the case of lipid-lowering, anti-hypertensive or anti-diabetic medications that are suspected to cause elevation of aminotransferases, patients will be eligible if treatment is associated with stable enzyme levels for at least 6 months and inclusion criteria 1a. and 1c. are both present.
- 4. Treatment with medications known to cause fatty liver disease such as atypical neuroleptics, tetracycline, methotrexate or tamoxifen
- 5. Uncontrolled hypo- or hyperthyroidism.
- 6. Decompensated advanced liver disease, defined as direct bilirubin > 0.5 g/dL, PT > 18", albumin < 3 g/dL, or history of ascites, encephalopathy, variceal bleeding, spontaneous bacterial peritonitis or liver transplant.
- 7. Active coronary artery disease, defined as persistent angina pectoris, reversible ischemia on cardiac stress test or imaging, or the presence of significant coronary artery disease on imaging or catheterization. Patients with coronary artery disease that was treated by angioplasty or bypass surgery may be eligible if they have no evidence of active disease >= 1 year after intervention, can safely stop antiplatelet and anticoagulant medications before the performance of invasive procedures, and have adequate ventricular function as assessed by echocardiography or cardiology consultation. These patients will require cardiology consultation and clearance prior to enrollment.
- 8. Congestive heart failure.
- 9. Chronic kidney disease, with creatinine clearance < 60 ml/min or eGFR < 60/ml/min/sq. m.
- 10. Uncontrolled diabetes mellitus. Patients may be enrolled if they have been on stable therapy with any anti-diabetic agent for at least 3 months prior to enrollment, are not foreseen to require antidiabetic medication or dose changes during the trial, and have an HbA1c <= 7.5% on enrollment.
- 11. Treatment with vitamin E. Patients who are currently taking vitamin E as a supplement will be requested to stop for at least 3 months before becoming eligible for enrollment. Patients who are taking vitamin E for a medical indication other than NAFLD will not be eligible.
- 12. Contraindication or inability to perform a liver biopsy.

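### Two exclusion thresholds carry wrong units: the bilirubin limb of criterion 6 cannot apply as written, and the eGFR limb of criterion 9, read per square metre, is 1.7 to 2.3 times the clearance limb beside it

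*Combined protocol and SAP*

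**What the plan says.** Both limits are in the list headed Exclusion criteria in the combined protocol and SAP.

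- **Item 6** defines decompensated advanced liver disease by any one of several findings. The first is "direct bilirubin > 0.5 g/dL". The others are a prothrombin time above 18 seconds and "albumin < 3 g/dL, or history of ascites, encephalopathy, variceal bleeding, spontaneous bacterial peritonitis or liver transplant".
- **Item 9** is headed chronic kidney disease and gives two alternatives joined by an or: "creatinine clearance < 60 ml/min" and "eGFR < 60/ml/min/sq. m".

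No other section restates either limit, gives the bilirubin limit in another unit, or names a reference body surface for the eGFR.

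**The concern.** These are operative thresholds that decide who enters the trial. An eligibility check that follows the text exactly would never trigger the bilirubin limb, and would hold the two kidney-function limbs to different levels although both carry the number 60.

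The bilirubin limb has a job to do. Compensated cirrhosis is not an exclusion: the section on monitoring and withdrawal provides liver-cancer surveillance and variceal endoscopy for participants with cirrhosis. Item 6 therefore draws the line between admissible and decompensated disease, in people who will have two or three percutaneous liver biopsies.

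The eGFR limb may be the one that matters at entry. The section on initial screening lists routine blood tests and bleeding time, while the "24-hour urine collection for creatinine clearance and protein and uric acid" is listed under the detailed in-patient assessment, after the run-in. That is an inference from the schedule, not something the protocol states.

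**Working it through.** The plan derives neither limit, so there is no figure of its own to reproduce. The check is unit conversion.

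**Bilirubin (item 6)**

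- Input: 0.5 g/dL, from item 6.
- Conversion: 0.5 g/dL × 1,000 mg/g = 500 mg/dL.
- Ratio to the same number in mg/dL: 500 / 0.5 = 1,000.
- Ratio to the albumin limit in the same item: 0.5 / 3 = 1/6. This shows the scale of the slip; it does not prove that the value is unattainable. That part is general laboratory knowledge and is not stated in the documents.
- A misread unit is unlikely. The inclusion criteria on the preceding lines give triglycerides, HDL cholesterol and glucose in mg/dL.

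**Kidney function (item 9)**

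- Inputs: 60 ml/min for creatinine clearance, with no indexing to body surface; 60 ml/min per 1 m² for eGFR, once the slash after 60 is dropped. With the slash kept, the unit has no meaning.
- Body surface area (BSA): the documents give none. I assume 1.7 to 2.3 m², and 1.6 to 2.4 m² as a wider check. The section on benefits says "Most patients with NAFLD are overweight and have some degree of insulin resistance", which points away from the low end. The 1.73 m² reference surface is a convention that the documents do not mention.
- Formula: limit in ml/min = 60 × BSA. The ratio to the clearance limit is 60 × BSA / 60 = BSA.

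| BSA (m²) | eGFR limit in ml/min | Ratio to 60 ml/min |
|---|---|---|
| 1.6 | 96 | 1.6 |
| 1.7 | 102 | 1.7 |
| 1.73 | 103.8 | 1.73 |
| 2.0 | 120 | 2.0 |
| 2.3 | 138 | 2.3 |
| 2.4 | 144 | 2.4 |

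As an illustration, treat clearance and eGFR as measuring the same thing. A patient with a BSA of 2.0 m² and a clearance of 100 ml/min passes the first limb, since 100 exceeds 60. The same value is 100 / 2.0 = 50 ml/min/m², which is below 60 and meets the second limb. Because the limbs are alternatives, the eGFR limb then governs and the clearance limb adds nothing.

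**If the index were per 1.73 m².** A clearance of 60 ml/min would equal 60 / BSA × 1.73. That is 64.9 at 1.6 m², 60.0 at 1.73 m², 51.9 at 2.0 m² and 43.2 at 2.4 m². On that reading the two limbs agree only at 1.73 m², so an indexed and an un-indexed limit with the same number still differ somewhat for larger or smaller patients.

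**The case against.** The strongest reply is that these are two misprints that no specialist liver clinic would follow. Results arrive in the laboratory's own units, and a bilirubin limit in g/dL would be seen at once as a slip. The repeated 60 in item 9 suggests that equivalent levels were meant. Nothing in the documents shows that anyone would be wrongly enrolled or turned away, and the endpoints, randomization, sample size and analysis do not depend on either limit. All of this stands, and it keeps the point small. It does not make the text right: the monitoring section says records will be checked against the protocol, so staff must either apply the printed limits or apply different, unwritten ones.

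Three stronger readings are tempting, and the documents do not support them.

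- *That the decompensation exclusion does nothing.* Only its bilirubin limb fails. The remaining limbs of item 6 operate, and items 12 (contraindication to biopsy), 14 (coagulopathy and low platelets) and 15 (which names severe cholestasis) give partial overlapping cover.
- *That the trial shuts out people with ordinary kidney function.* The thresholds sit under a heading of chronic kidney disease, which on a natural reading limits whom they catch. The eGFR unit is also too garbled to establish firmly that a limit of 102 to 138 ml/min was set.
- *That the two kidney limbs contradict each other.* They are joined by an or, so both can be applied. One is stricter than the other; that is a mismatch, not a logical conflict.

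A character lost when the PDF was turned into text cannot be ruled out for the eGFR string, though nothing marks a gap there.

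**Conclusion.** The point holds as a correction to two eligibility units. As printed, the bilirubin limit is 500 mg/dL and that limb can never apply, given the general knowledge that such a serum value does not occur. The eGFR limit has a garbled unit; read per 1 m², it is 1.7 to 2.3 times the clearance limit for an assumed BSA of 1.7 to 2.3 m², and 1.73 times at the conventional reference surface. The size of the mismatch rests on the assumed body surface and on dropping the stray slash. The practical effect is probably small and the statistical analysis is unaffected. It is still worth correcting, because these lines decide entry and nothing elsewhere in the protocol repairs them.

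**What to change.** In item 6, restate the bilirubin limit in the unit the clinical laboratory reports. In item 9, remove the stray slash, state the eGFR unit with its reference body surface if it is indexed, and reconcile the two limbs so that they describe the same intended level of kidney function. Since an indexed and an un-indexed limit of 60 do not coincide at every body size, the item should also say which measure is used at screening, or that meeting either one excludes. The sponsor sets the clinical levels; none is proposed here.

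The cost is a change to two lines of the eligibility list, plus a check that any screening checklist uses the corrected units. No recalculation of sample size or change to the analysis is needed. If enrollment has begun, a short note of the units actually applied would document past decisions.
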